# Abbreviations

ASD	Autism Spectrum Disorder
VR	Virtual Reality/active video games
ASSQ	Autism Spectrum Screening Questionnaire
n	Number of participants
EHI-SF	The Edinburgh Handedness Inventory-short form
3D	Three Dimensional
PBS	Pediatric Berg's Balance Scale
HR	High resolution
Hz	Hertz
GCP	Good Clinical Practice
GLP	Good Laboratory Practices
m	Meter
sec	Seconds
min	Minutes
mm	Millimeter
ANOVA	Analysis of Variance
SPSS	Statistical Package for the Social Sciences
IDE	Investigational Device Exemption
IRB	Institutional Review Board
ISO	International Organization for Standardization
HIPAA	Health Insurance Portability and Accountability Act
IB	Investigator's Brochure
AE	Adverse Event
CFR	Code of Federal Regulations
OHRP	Office for Human Research Protections
PI	Principal Investigator
SAE	Serious Adverse Event
SAP	Statistical Analysis Plan
SMC	Safety Monitoring Committee
L	

SOA	Schedule of Activities
SOP	Standard Operating Procedure
UP	Unanticipated Problem
US	United States
DCC	Data Coordinating Center
DHHS	Department of Health and Human Services

This tool also presents an opportunity to provide youth with ASD an effective, enjoyable, and cost-effective balance intervention. Postural control/balance training should be based on the proven theories of motor learning and motor control 16,17. Preliminary studies in people with ASD have used various techniques such as using a robotic arm to move a target on the screen 18, wearing prism goggles 18, video modelling and video feedback 19, music therapy 20 to explore the following motor learning theories: implicit and explicit learning 18,21, feedback-based mechanisms 19,22, principles of joined movements 20, and goal directed movements with the knowledge of results and performance 16. Most of these studies were based on non-randomized, non-controlled, and/or preposttest designs and thus the findings are insufficient to provide evidence regarding which of the motor learning theories is most effective for designing an intervention 23.

The foundation of many VR active games involve motor learning/control tenets as the require an individual to control their center of gravity over the base of support to successfully complete game-required movements, consequently providing an opportunity for training postural control skills. It has been shown to be effective in improving static and dynamic balance in those with ASD and other types of disabling conditions such as developmental coordination disorder and cerebral palsy. The therapeutic elements of VR active gaming typically incorporate the motor learning principles of feedback and task-specificity. Also, therapeutic VR tools engage the person in repetitive motor practice at variable intensity by constantly providing knowledge of performance and knowledge of results. These components of neurorehabilitation help in facilitating restoration of movement capabilities and some studies have reported the potential of VR to alter neuroplasticity. Additionally, VR active gaming provides variability of learning by allowing multiple tasks at varying difficulty targeting center of pressure movement of the individual's body to emphasize dynamic balance skills, while also maintaining high levels of interest and motivation which is required for promoting adherence to the intervention. Virtual reality active gaming enables the delivery of a stimulus in a standardized and reproducible manner and can be adapted according to the participant's needs. This approach also utilizes visual and proprioceptive information which are often heavily relied upon for maintaining balance by individuals with ASD. Despite the fact that VR active gaming incorporates scientific mechanisms for improving balance, there exist few, evidence-based best practices that use this method to address balance in youth with ASD.

In addition to being based on principles of motor learning/control, commercially available VR active gaming can be a cost-effective, at-home intervention. Commercially available systems cost from \$200 to \$1000 for the consoles with an additional \$50 to \$100 for individual games, which could be a one-time investment. About 67% of U.S (United States). households already own at least one VR system^34 and, if there is valid and reliable evidence to support therapeutic outcomes, insurance may pay for these devices. Additionally, children tend to enjoy active gaming and this approach may provide an advantage over traditional therapeutic approaches regarding various accessibility issues (e.g., transportation issues), adherence, and at-home use. Therefore, VR active gaming should be explored further as a stand-alone treatment or an adjunct to conventional balance rehabilitation approaches.

There are few well designed studies using VR-based interventions to address balance in children and youth with ASD. Previous research in this area consists mainly of quasi-experimental studies , which, although useful in providing descriptive information, are limited in providing strong, best-practice evidence. These studies have demonstrated improvements in certain balance variables such as one- and two-footed balance, heel-toe walking distance, and balance components of certain clinical motor assessments (e.g., Movement Assessment Battery for Children-2nd ed, Bruininks-Oseretsky Test of Motor Proficiency, 2nd ed).

To date only two control group design studies have used VR active gaming-based interventions to improve balance in individuals with ASD. Milajerdi and colleagues compared three conditions in children with ASD (n=20 per group): physical activity intervention, active video gaming, and usual therapies. After 24 sessions over 8 weeks, throwing and catching skills, but not balance skills, improved and there were no differences between conditions. There are several factors that may have contributed to the lack of significant balance skill improvement in this study. First, only one VR game (tennis) was used, and this can be played standing with minimal center of pressure movement, also reducing the variability of training and variability in the task, and consequently restricting motor learning. Second, only providing one game option does not allow for choice and this can impact motivation, participation, and engagement. Third, adherence, enjoyability, and motivation were not reported and therefore no conclusions could be drawn regarding either retention of treatment effects or long-term use.

Caldani and colleagues used an open-case control design to test the hypothesis that short-term balance training using VR would lead to neuroplastic changes in the cerebellum leading to

improvements in postural control in youth with ASD. They compared the effect of 6 minutes of postural control training using 2 customized active-video games with 6 minutes of rest between each trial (n=20 each in intervention and control groups). The specifically designed game consisted of moving a dot on a screen, which represented the participant's center of pressure. The subject moved the dot to either a pre-defined target or to avoid the pre-defined target by standing on a force platform. The control group rested for the duration of the intervention. The researchers reported a reduction in postural sway immediately after the intervention under both eyes open and eyes closed conditions but speculated that the changes were due to test-retest. This outcome could have been predicted and it is unfortunate that the researchers did not plan for this accordingly. This test-retest response limits translation of the intervention over longer duration as the dose, that is duration of the intervention, is insufficient to cause behavioral changes.

Overall, out of the five studies using VR active gaming interventions in youth with ASD, including the previously described studies using some type of control group, three reported it to be beneficial for improving balance and two were inconclusive. Findings from all of these studies are compromised due to 1) lack of randomized controlled trials, 2) lack of objective balance measures, 3) variability in intervention duration, 4) small sample sizes (10-29 subjects), 5) limited game options, 6) lack of clear identification of motor learning/control principles in the research design, (7) variability in game design (i.e. 3 were not commercially available), and 8) no assessment beyond immediate-post intervention. The current published literature does not provide sufficient evidence for the use of VR active gaming as a modality to address postural control/balance deficits in individuals with ASD.

The purpose of this study is to deliver a VR active gaming-based static and dynamic balance intervention to children and youth with ASD that addresses several of the aforementioned gaps in the literature by: 1) using a controlled clinical trial design, 2) using objective measures of static and dynamic balance, 3) using select commercially available VR active games that incorporate specific motor learning principles that impact balance, 4) using a participant sample based on a power calculation to ensure a robust statistical analysis, and 5) assessing retention effects 4 weeks post-intervention. Addressing these gaps will significantly contribute to the knowledge base by verifying if VR active gaming interventions are effective in improving static and dynamic balance in youth with ASD.

## 2.0 Objectives

# 2.1 Primary Objective

H1: Participation in VR active video gaming incorporating explicit and implicit learning, feedback and knowledge of results, and knowledge of performance motor tenets will lead to increased postural control, as reflected by improved static and dynamic balance. This hypothesis will be tested by Specific Aim 1: to assess the effect of a short-term (3 days/week for 2 weeks) VR active video gaming intervention on static balance, versus traditional balance training exercises, in youth with ASD.

H2: Participation in VR active video gaming incorporating explicit and implicit learning, feedback and knowledge of results, and knowledge of performance motor tenets will reduce the deviation in the spatiotemporal parameters of the gait due to increased dynamic balance and improved motor coordination. This will be tested by Specific Aim 2: to assess the effect of a short-term (3 days/week for 2 weeks) VR active video gaming intervention on spatiotemporal parameters of gait, as a measure of dynamic balance, versus traditional balance training exercises, in youth with ASD.

# 3.0 Outcome Measures/Endpoints

# 3.1 Primary Outcome Measures:

- 1. High resolution pressure mat: Static balance will be objectively measured using an HR Mat pressure mat (Tekscan Inc.). The center of pressure will be measured at 100Hz using the center of pressure coordinates by inbuilt software. The area of the postural sway and direction of the sway will be measured as indicators of static balance with participants standing on the pressure mat with hands at their side under 2 conditions: eyes open and eyes closed for 30 seconds each condition. A member of the research team will stand beside the participant and provide balance support as needed.
- 2. Qualisys Motion Capture system: Step length, stride length, step-width, double support period, cadence and velocity are the gait parameters that will be measured as indicators of dynamic balance using Qualisys motion capture system. The

Qualisys motion capture system will be used to assess gait as a measure of dynamic balance. The system is composed of 13-infrared cameras that capture light reflected by passive markers at a frequency of 100 Hz. It is a reliable and a valid tool for gait assessment. The biomechanical model of feet will be constructed using Visual 3D software for gait analysis. Participants will wear the same sneakers/sports shoes for each assessment. Nine markers will be placed bilaterally (18 total) at the following points: distal aspect of the great toe, 1st metatarsal, 5th metatarsal, top of the foot, medial malleolus, and lateral malleolus, proximal heel, distal heel, and lateral heel. A comfortable walking speed for each participant will be recorded using a stopwatch to measure the time it takes them to walk back and forth on a 15-meter-long-platform 3 times and the average of the 3 trials will be calculated. Participants will then walk at the same speed at least 5 times or until the entire gait cycle is captured by the infrared camera system twice. Gait cycle is defined as heel-strike to heel strike on the dominant foot. A couple of practice trials will be performed to ensure understanding of the procedure and verbal prompting will be used to remind the participant to walk typically. Biomechanical models of feet will be constructed using Visual 3D software for gait analysis. If the participant is unable to perform this assessment as described, it will be rescheduled up to two times before study dismissal.

3. Pediatric Balance Scale (PBS): The PBS will be used to assess static and dynamic balance. It is a valid and reliable clinical balance assessment tool for children and youth with motor impairments. It is a 14-component battery that evaluates daily living tasks such as sitting to standing, transferring from one chair to another, and sitting and standing without support. Item numbers 1-3 and 9-14 are specific to dynamic balance while item numbers 4-8 are specific to the static balance. Participants are graded as 0-4 on each component of the scale with 56 being the highest total score achieved. A higher score indicates better postural control. Interpretation of the scores is as follows: 41 to 56 denotes a low fall risk, 21 to 40 a medium fall risk, and 0 to 20 a high fall risk. The PBS takes fifteen to twenty minutes to administer. A different researcher from the study team will record the PBS to

avoid any assessment bias. The researcher will demonstrate each task and the participant will be allowed 1-2 practice trials before official assessment as per the instructions provided in the tool. The researcher is well trained in administrating the PBS. Inter- and Intra-rater reliability will be checked at least four times throughout the course of the study by scoring a videotaped administration of the tool. An intraclass correlation of 0.9 must be achieved to avoid retraining on the PBS.

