# 3.2 End points:

- 1. Primary endpoints: Reduction in PBS total score by 3.7 points. This is in accordance with the MCID range reported by Chen et al, 2013 as 3.66-5.83 for PBS in children with neuromotor impairments.
- 2. For static balance: 1) reduction in the sway area of 95% confidence ellipse for center of pressure, 2) reduction in mediolateral direction of the postural sway.
- 3. For dynamic balance: Reduction in 1) step width, 2) double support period. Increase in 1) step length, 2) Cadence, 3) Gait velocity
- 4. Secondary endpoints: Safety.

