# 4.0 Eligibility Criteria

#### 4.1 Inclusion Criteria

- a) age 7-22 years,
- b) existing ASD DSM-5 level 1 or 2 diagnosis confirmed by medical record/ educational services categorized under ASD/ therapeutic services categorized under ASD/ any other official document indicating the diagnosis of ASD,
- c) able to follow instructions and
- d) able to stand unsupported for at least 20 minutes.

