# 11.0 Statistical Considerations

According to prior research study examining the similar paradigm using Xbox games (Ghobadi et al. 2019), we predict the medium effect size (f=0.25) to detect significant changes within groups, between groups and effect of timepoint on static and dynamic balance. Power analysis

(using G\*power 3.1.9.7 software) indicates 14 subjects in each group to have 0.8 power to detect this effect (alpha 0.05). To account for the likelihood of attrition and noncompliance, total 40 participants are being recruited. Data from participants who engage in all the intervention sessions will be included in the analysis.

SPSS (Statistical Package for the Social Sciences) and MATLAB will be used for processing and analyzing the data. Participants demographic and health characteristics will be compared using paired sample t-tests. Intention to treat analysis will be used for addressing effects of treatment or control on static and dynamic balance. The dependent variables for static balance include: 1) sway area of 95% confidence ellipse for center of pressure(mm²), 2) direction of center of pressure sway as anteroposterior and mediolateral (mm). The dependent variables for dynamic balance are: 1) step length (m), 2) stride length (m), 3) step width (m), 4) double support period (sec), 5) cadence (steps/min) and 6) gait velocity (meters/min). Total PBS score will be dependent variable for both static and dynamic balance.

Two-way repeated measures ANOVA (analysis of variance) will be used to determine 1) within intervention and control group, for assessing the main effect of group, 2) between intervention and control group for assessing main effect of time, and 3) between - within interaction for assessing the interaction term. Statistical significance will be declared if  $p \le 0.05$  (two-tailed).

[name] ([contact]) will assist with the statistical considerations.

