# 12.0 Data Management

Qualisys motion capture system, visual 3D and HR mat use the inbuilt software for collecting and cleaning the data. HR mat data will be exported to MATLAB for analysis of postural sway. The data will be stored on an access-controlled computer situated in laboratory 70 E of the School of Public Health building in Indiana University Bloomington. Only approved study personnel will have access to this data.

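### Balance support is allowed during the 30-second sway recordings, and no rule marks, repeats or sets aside a recording in which it was given

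*Combined protocol and SAP*

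**What the plan says.** Section 3.1, item 1, measures static balance on the pressure mat under two conditions: "eyes open and eyes closed for 30 seconds each condition". The sentence that follows is "A member of the research team will stand beside the participant and provide balance support as needed". Section 7.0 (2.4) repeats both as the operating procedure, and item 4 of Section 7.0 applies the same assessment at sessions 8 and 9. The permission therefore covers baseline, post-intervention and retention.

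Section 3.2 counts as benefit a "reduction in the sway area of 95% confidence ellipse for center of pressure", and also less mediolateral sway.

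On data handling, Section 12.0 says "Qualisys motion capture system, visual 3D and HR mat use the inbuilt software for collecting and cleaning the data" and "HR mat data will be exported to MATLAB for analysis of postural sway". The only inclusion rule in Section 11.0 that looks at conduct concerns attendance: "Data from participants who engage in all the intervention sessions will be included in the analysis". Eligibility (Section 4.1) requires that a participant be "able to stand unsupported for at least 20 minutes".

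**The concern.** The sway endpoint is meant to show how steadily a participant stands unaided. Once someone gives physical support during the recording, the centre-of-pressure trace reflects the participant and the helper together. The procedure allows this and gives the analyst no way to see it, because the contact is not recorded.

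The error is also not random noise. Support given on need goes to the participants with the most sway, and the need should lessen if their balance improves. A participant supported at baseline but not later would be compared with an invalid starting value. Section 5.0 describes blinding of participants, and the static-balance text does not say whether the team member beside the mat knows the allocation. The plan therefore also gives no assurance that support is given equally in the two arms.

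**Working it through.** **Is there a rule for a supported recording?** The places where one could stand, in turn:

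- Section 3.1, item 1, and Section 7.0 (2.4): support is permitted; nothing on stopping, repeating, marking or logging.
- Section 7.0, item 4, and the Study Calendar: the assessment is repeated; nothing added.
- Section 3.1, item 2: "If the participant is unable to perform this assessment as described, it will be rescheduled up to two times before study dismissal". This belongs to the motion-capture gait assessment. It concerns new appointments and then dismissal, and it is not repeated for the mat.
- Section 11.0: attendance only; nothing on the validity of a recording.
- Section 12.0: software cleaning and export only; no flag or exclusion.

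No rule was found.

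**Size for one participant.** The documents give no sway values, no support frequency and no effect of contact on the reading, so every input here is an assumption. Let true sway be 1000 mm² at baseline and 800 mm² at follow-up, let only the baseline recording be supported, and let support multiply the reading by k.

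- True change: (800 − 1000) / 1000 = −20%.
- Recorded change: (800 − 1000k) / (1000k).

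| k | Baseline recorded (mm²) | Recorded change |
|---|---|---|
| 1 (no support) | 1000 | −20% |
| 0.75 | 750 | 50/750 = +6.7% |
| 0.5 | 500 | 300/500 = +60% |
| 0.33 | 330 | 470/330 = +142% |
| 1.5 (contact raises sway) | 1500 | −700/1500 = −46.7% |

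The sign turns at k = 800/1000 = 0.8. Any support that lowers the baseline reading by more than 20% makes this improvement look like a worsening.

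The pattern of support matters as well. With k = 0.5 at both visits, the record is 500 then 400 mm². The percentage change is right (−20%), but the change in mm², the unit listed in Section 11.0, is −100 instead of −200. With k = 0.5 at follow-up only, the record is 1000 then 400 mm², a 60% fall that overstates the improvement.

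**Group level.** The distortion of an arm mean depends on the share of participants supported, on k, and on the visits at which support occurs. The documents give none of these, so no group-level figure is offered. The sample size in Section 11.0 does not bear on the point.

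**The case against.** The sentence can fairly be read as describing a safety spotter, like the caregiver and chair used during home sessions. Participants must be able to stand unsupported for 20 minutes, and Section 4.2 excludes a documented balance disorder, dizziness, muscle weakness and need for assistance to stand. The task is 30 seconds of quiet standing after practice trials. Contact should be uncommon, and when it occurs its direction is not certain. Section 3.2 names the Pediatric Balance Scale total as the primary endpoint and lists sway separately.

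Most of this stands. It limits how often the problem arises and how much weight it deserves. It does not close the gap. The text provides for support, not only for standing by. The eligibility criteria do not mention standing with eyes closed. Section 3.1 lists the mat among the primary outcome measures, and Specific Aim 1 concerns static balance. If contact is rare, a log would show it; without one, nobody could tell.

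A reader might infer that staff hold participants up during the test. The documents do not say so: the kind of support is left undefined. A reader might also infer that the protocol directs supported recordings into the analysis. It does not; it is silent on them.

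**Conclusion.** The point holds as a gap in the measurement procedure. Support is permitted in both recording conditions at all three assessments, and nothing identifies or handles the recordings affected. Such a recording is invalid as a measure of unaided sway whichever way contact moves it, and because contact is not logged the fault could not be repaired at analysis.

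For an individual the effect can be large: under the assumed values, a true 20% fall is recorded as a 60% rise. For the trial it is unknown and probably limited, since eligibility makes support unlikely for most participants.

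It is tempting to go further and say that the least stable participants will have falsely low sway, or that the treatment effect will shrink by a given fraction. The documents support neither. Lower readings are the likelier result of contact, but a stumble or grasp could enlarge the ellipse, and any fraction would rest on an assumed frequency of support.

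**What to change.** Leave the spotter and the safety support instruction as they are. Add to Sections 3.1 and 7.0 (2.4):

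1. Any physical contact during a mat recording is logged by condition (eyes open or closed), visit and arm.
2. A recording with contact is not used as a sway value. The 30-second trial is repeated at the same visit where feasible.
3. If no contact-free recording is obtained, the sway value for that condition and visit is treated as missing because of inability.

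Add to Section 11.0:

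4. Counts of contacted recordings, and of conditions with no valid recording, are reported by arm and visit.
5. A sensitivity analysis gives the values missing through inability an unfavourable outcome, for example a rank-based comparison of change between arms with worst rank. The worst rank should attach to the visit at which the inability occurred, so that a participant unable at baseline and able later is not counted as having worsened. This stands beside the planned repeated measures ANOVA and does not replace it.

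The cost is a few sentences, one data field and an occasional extra 30-second trial. The downside is a few missing sway values. Section 11.0 gives no method for missing values, so the treatment of these should be stated with the change.
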